HRP-503B – BIOMEDICAL RESEARCH PROTOCOL
(2017-1)

Protocol Title: Guanfacine to Improve Substance Use Outcomes in Women
HIC#: 2000023100

Principal Investigator: [name] PhD

Version Date: April 2018

(If applicable) **Clinicaltrials.gov Registration #:** Click or tap here to enter text.

SECTION I: RESEARCH PLAN

- Statement of Purpose:** State the scientific aim(s) of the study, or the hypotheses to be tested.

We hypothesize that Guanfacine (GUA) (3mg/day) will reduce drug craving, improve cognitive flexibility and result in associated lower drug use in women with substance use disorder (SUD) in an outpatient clinical setting. This study proposes to extend our previous Phase I experimental work to address the following specific aims: (1) assess GUA's target engagement of drug craving and cognitive flexibility in a laboratory challenge session and in a 10-week outpatient clinical study, (2) demonstrate target validation by showing that reduced drug craving and improved cognitive flexibility will predict lower drug use outcomes during the 10-week clinical trial in SUD women, and finally, (3) evaluate data replication and scalability of GUA target effects across two clinical sites (Yale and SUNY-Stony Brook).

- Probable Duration of Project:** State the expected duration of the project, including all follow-up and data analysis activities.
3 years followed by 2-years data analysis
- Background:** Describe the background information that led to the plan for this project. Provide references to support the expectation of obtaining useful scientific data.

Growing basic evidence indicates that the alpha-2 adrenergic agonist, guanfacine (GUA) decreases drug-related striatal-limbic up-regulation and stress sensitization resulting in drug cue and stress-induced reinstatement in laboratory animals (Shaham and Hope, 2005), and also improves neurocognitive abilities such as attention, flexibility, working memory and decision making (Arnsten, 2009). In NIDA-supported medications development work (R01-DA027130, PI: [name]), we identified in a 3-day inpatient laboratory controlled experiment that GUA at 3mg/day dose engaged target drug craving and cognitive flexibility processes, and more importantly, that GUA engaged these key processes in a sex-specific manner with

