positive effects in women but not in men (Fox et al., 2012; [name] et al., 2011). Preliminary data also showed that GUA 3 mg/day (bid dosing) vs. placebo led to higher cocaine-negative urines in an 8-week outpatient setting only in women and not men.

4. **Research Plan:** Summarize the study design and research procedures using non-technical language that can be readily understood by someone outside the discipline. **Be sure to distinguish between standard of care vs. research procedures when applicable, and include any flowcharts of visits specifying their individual times and lengths.** Describe the setting in which the research will take place.

The current study will test **GUA (3 mg/day) vs Placebo (PBO)** in a 10-week clinical trial across 2 sites in a total of 100 SUD women.

All participants will be titrated to steady-state medication levels over 2 weeks followed by a **7-week treatment period using a standard cognitive behavioral relapse prevention** with medication management and contingency management (CM) for treatment attendance. A 5-day taper will be implemented in week 10. All participants will also take part in **two laboratory challenge test sessions**: one at pre-treatment (pre-tx) and one during week 9 of treatment, to assess provoked drug craving and cognitive flexibility under stress, drug cue and neutral cue conditions in a randomized and counterbalanced order.

Pre-treatment Intake Procedures: Following the initial telephone screening, eligible participants will meet with the research staff to obtain written informed consent. Subjects will complete 2-3 intake appointments, and during these appointments they will be consented, screened of substance use, and provide demographic and psychiatric data. Physical examinations, blood work, a urine test, and a breathalyzer test will also be completed. All subjects will meet with the study physician, and if deemed eligible, after discussion of risk and benefits, subjects will be randomized into the study.

Randomization: Eligible subjects will then be randomized in a double blind manner to either placebo or 3 mg/day (bid dosing) of GUA balancing the patients on age, education, race, ADHD and severity of drug use.

Medication Titration Period (wk 1-3): Following a 3-day abstinence period, a 2-week titration period, previously found to be safe and with only mild adverse effects (Fox et al., 2014; Fox et al., 2012; Milivojevic et al., 2017) will be initiated (see Table 1).

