Laboratory Challenge Component: An identical laboratory challenge session will be conducted in the initial week of outpatient treatment Week 0, prior to medication, and again in Week 9. Our standard imagery script development procedures will be used to develop the stress, drug cue and neutral relaxing imagery scripts. The stress imagery script will be based on participants' description of a recent personal event experienced as "most stressful", and determined as such by rating it above 8 on a 10-point stress scale. These may include breakup with a significant other, marital conflict or job-related stress. A drug cue script will be developed based on situations involving people places and things pertaining to drug use that led to wanting drug and eventual drug use (e.g., meeting drug using friend, going by a favorite bar, etc). The neutral script will be developed from a personal non-alcohol-related relaxing situation. A 5-minute 'script' of each scenario will be written using Scene Construction Questionnaires ([name], 2009) where verbal and non-verbal responses, and physiological and bodily sensations regarding the events will be obtained. A script is then written following standard format and content procedures and scripts are then recorded onto audiotape for guided imagery in the laboratory sessions ([name], 2009). On the morning of the day prior to the initial laboratory session, participants will be brought into the testing room to receive training in relaxation and imagery procedures, as well as familiarize themselves with the subjective rating forms. The 10-min relaxation training will comprise muscle relaxation procedures in order to help subjects reach a relaxed state prior to imagery exposure during the laboratory sessions.

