Neutral Imagery Condition (Condition 2)	
3:40 PM	Schedule as in condition 1
Stress / Drug Cues (Condition 3)	
4:20 PM	Schedule as in condition 1

Order of imagery conditions is counterbalanced across subjects.

Study Assessments: Assessments include the following:

- 1) Sample description and eligibility including sociodemographics; psychosocial, substance use, and medical history; psychiatric assessment using the:
 - i) Structured Clinical Interview of Diagnostics (SCID-I) for DSM-V,(First et al., 1995),
 - ii) Connors ADHD Assessment and Rating Scale (CAARS,(Conners, 1999)
 - iii) vitals
 - iv) CBC, blood chemistry
 - v) urinalysis
 - v) pregnancy testing;
- 2) Primary SUD outcomes assessed using the:
 - i) Substance Use Calendar (SUC) developed by Miller and Del Boca (Miller and Del Boca, 1994) and based on the Time-Line Follow-Back (Sobell and Sobell, 1992; Sobell et al., 1996) and urinalysis for objective drug use assessed 2X/weekly during the 10 week period (20 urines);
- 3) Secondary Outcome Measures assessing drug craving using the standard brief versions of the Drug Craving questionnaires for cocaine (Cocaine Craving Questionnaire: CCQ,(Tiffany et al., 1993), cannabis (Marijuana Craving Questionnaire: MCQ, (Heishman et al., 2009)), alcohol (Alcohol Urges Questionnaire: AUQ, (Bohn et al., 1995) and nicotine (Questionnaire of Smoking Urges: QSU(Tiffany et al., 1993); (Tiffany and Drobes, 1991). Drug abstinence symptoms using standardized cocaine selective severity assessment (CSSA, (Kampman et al., 1998), Clinical Alcohol Withdrawal Assessment-Revised (Sullivan et al., 1989); The Cannabis Withdrawal Scale (Allsop et al., 2011); and the Minnesota Nicotine Withdrawal Scale (MNWS; (Hughes et al., 1986). Other drug use and drug related problems will be measured using the SUC; urinalysis; breathalyzer; the Addiction

Severity Index (ASI; (McLellan et al., 1992)) and Treatment Services Review (McLellan et al., 1992); stress (Perceived Stress Scale; (Cohen et al., 1983)); anxiety (Hamilton Anxiety Rating Scale, Ham-A; (Hamilton, 1960)) and depressive symptoms (Hamilton Depression Rating Scale, Ham-D, (Hamilton, 1960)). cognitive flexibility will be assessed using the Stroop Color Word Test; (Golden, 1975),

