Data Management: Data entry will be conducted using the Web-based REDCAP direct data entry system. Both sites are fully trained and running with REDCAP and have implemented this platform in clinical outcome studies with SUD samples. Utilizing the REDCAP system will allow data to be directly collected into the Yale managed web-based system across sites with no identifying information transmitted over the internet. Field validation (e.g. no out of range/invalid responses accepted) and form validation (e.g. logically impossible responses to different questions) are built into the REDCAP system and the study data manager will conduct weekly quality control and data management. After online reviews, the data are archived onto servers and password protected with only certain members of the team having appropriate level of data access. All quality control and management issues will be addressed immediately and also discussed in the across site weekly study meetings.

Data Analysis: Data analysis will be performed under the direction of Project PIs in consultation with [name], the Yale biostatistician. Screening for data entry errors, outlier checks and assessment of missing data and testing of normality assumptions will be conducted. Transformations will be applied as necessary. We will compare the treatment groups on demographic and clinical variables using t-tests/chi-square analyses as appropriate. If any group differences are found, the specific variable will be entered as a covariate in all specific analyses. For the primary outcome, we will use significance level of 0.05. Significance levels for secondary outcomes will be adjusted using Bonferroni correction for number of analyses performed.

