Adequacy of Sample Size: Sample size estimates are limited by the fact that there are no previous clinical outcome studies of GUA/PBO in SUD women. As shown in above, data from our previous work with GUA yielded highly significant sex X med group effects for target engagement measures of drug craving and Stroop improvements with moderate to high effect sizes (f^2 's ranging from 0.39-1.22). Using the GUA/PBO preliminary data from the 8-week pilot trial, percent of negative cocaine urines were 40.18% versus 67.86% in PBO vs GUA for the whole group (large effect size $d=0.76$), with 53.12% versus 100% for PBO vs. GUA in women ($d=1.0$) and 35% vs 55% negative urines in placebo vs guanfacine in men ($d=0.628$). Thus, assuming power=0.80, and at $p<0.05$, α level of 0.05, sample size estimates indicate that we will need 40 subjects per cell (Medgroup) to assess GUA/PBO in clinical outcome hypotheses in Aim 2 and Aim 3. This sample size allows for detection of medium effect sizes ($f=0.25$, Cohen) with more than 80% power assuming α level of 0.05 for the main effect of medication group on the primary outcome variable. Assuming an α level of 0.01 to correct for multiple tests for the secondary outcome measures we can detect effects in the medium range ($f=0.28$) with 80% power for all the main effects for secondary outcome variables. Including a 20% attrition rate, we propose an N=50 per group for a total N of 100 (50 per site).

SECTION II: RESEARCH INVOLVING DRUGS, BIOLOGICS, RADIOTRACERS, PLACEBOS AND DEVICES

If this section (or one of its parts, A or B) is not applicable, check off N/A and delete the rest of the section.

A. RADIOTRACERS

N/A

B. DRUGS/BIOLOGICS **N/A**

1. If an **exemption from IND filing requirements** is sought for a clinical investigation of a drug product that is lawfully marketed in the United States, review the following categories and complete the category that applies (*and delete the inapplicable categories*):

Exempt Category 1: The clinical investigation of a drug product that is lawfully marketed in the United States can be exempt from IND regulations if all of the following are yes:	
1. The intention of the investigation is NOT to report to the FDA as a well-controlled study in support of a new indication for use or to be used to support any other significant change in the labeling for the drug.	

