In the previous work with 3-week treatment of GUA (3mgs/day) versus placebo discussed above, [name] found it to be safe and well tolerated. In the initial study (25), the most common side effects were mild tiredness and fatigue (guanfacine 24%; placebo: 8%) and headaches (guanfacine 18%; placebo 8%). All symptoms dissipated over time without further intervention. Side effects from a dose-ranging study comparing placebo, 2 and 3 mg/day of guanfacine (26) (106) indicated mild symptoms which dissipated rapidly without intervention in 7/21 individuals in the placebo group (33.33%), 5/12 individuals in the guanfacine (2mg) group (41.7%) and 4/11 individuals in the guanfacine (3mg) group (36.4%). Furthermore, there were no significant blood pressure differences across medication and placebo groups. Also, there were no significant sex differences in reported side effects.

In preparation for this proposal, [name] conducted a randomized, double-blind, 8-week pilot study of GUA (3mgs/day) with treatment seeking CUD men and women (n=7: 5M/2F) vs placebo (n=7: 4M/3F). Using the same 16-day titration schedule used previously and proposed in the current project, GUA plasma levels were assessed as at weeks 4 and 8 in the outpatient study as well as in the inpatient study described above. GUA levels obtained in the outpatient pilot were comparable to levels to those from the inpatient study described above. These data suggest that generic GUA with bid dosing was acceptable, and patients showed high medication compliance in the outpatient setting.

Together, data indicates guanfacine 3 mg/day to be safe and tolerable with regard to assessing target engagement and validation across multiple sites in SUD women.

3. **Source:** Identify the source of the drug or biologic to be used.

GUA pills will be obtained from Watson Pharmaceuticals by the Investigational Drug Service (IDS) at Yale-New Haven Hospital (YNHH). The research pharmacist will make up identical active and placebo capsules for medication administration for both sites. Medications will be shipped to Stony Brook from Yale for randomization and dispensing at the Stony Brook site. Medication administration will occur at 8am and 8pm each day to standardize the time of administration.

a) Is the drug provided free of charge to subjects? YES NO
If yes, by whom? IDS at YNHH

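### The only stated covariate rule is triggered by baseline differences, so the five factors that randomisation balances would rarely be adjusted for, which forgoes power if they predict outcome

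*Combined protocol and SAP*

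**What the plan says.** Section I, 13 (Statistical Considerations, Data Analysis) sets a two-step procedure. First: "We will compare the treatment groups on demographic and clinical variables using t-tests/chi-square analyses as appropriate". Then: "If any group differences are found, the specific variable will be entered as a covariate in all specific analyses". It does not say what counts as a difference, which or how many variables are tested, or what model is used for the primary outcome.

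Section I, 4 (Research Plan, Randomization) allocates women double-blind while "balancing the patients on age, education, race, ADHD and severity of drug use". The balancing method is not described. No section commits these five factors to any outcome model.

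Site is not in the balancing list, although Aim 3 in the Statement of Purpose is to "evaluate data replication and scalability of GUA target effects across two clinical sites". Section II, B (Source) says "Medications will be shipped to Stony Brook from Yale for randomization and dispensing at the Stony Brook site". That suggests allocation happens at each site, but the document does not say whether site is a randomisation stratum.

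**The concern.** The two rules pull against each other. The factors judged important enough to balance are the ones that a difference-triggered rule is least likely to pick.

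Balancing on a factor that predicts outcome removes most of that factor's contribution to the true variance of the treatment comparison. A model that omits the factor still counts the contribution as residual error. The standard error is then too large, the test is conservative, and the precision that balancing could have delivered is not used.

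For variables that are not balanced, the problem is pre-specification: chance decides which covariates enter, so the model behind the reported estimate is fixed only after baseline data have been seen.

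**Working it through.** **1. The plan's own sample size.** Inputs from Section I, 13 (Adequacy of Sample Size): 40 per group, alpha 0.05, power 0.80, 20% attrition, and pilot effects d=1.0 (women), 0.76 (whole group) and 0.628 (men). Two-sided testing is assumed.
- 40/(1-0.2) = 50 per group reproduces.
- 40 per group follows from d=0.628: n = 2(1.96+0.842)²/0.628² = 39.8.
- The same section says "This sample size allows for detection of medium effect sizes", f=0.25, with more than 80% power. With d=2f=0.5 and 40 per arm, d√(n/2) = 0.5×√20 = 2.236, and power is Φ(2.236-1.96) = 0.61 (0.60 by the t distribution). The claim does not reproduce for a single two-arm comparison. That is a separate matter; d=0.5 is used here only as the plan's own benchmark.

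**2. How often the rule would select a balanced factor.** Without balancing, five independent factors tested at 0.05 give 1-0.95⁵ = 22.6% for at least one. With simulated minimisation the figure is 0.3% to 3.9%, depending on whether age, education and severity are dichotomised or continuous and whether balancing is overall or within site.

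**3. Closed form under perfect balance.** Let R2 be the share of outcome variance that the five factors explain. It is not in the documents, so a range is shown.
- Type I error, unadjusted: 2[1-Φ(1.96/√(1-R2))]
- Power, unadjusted: Φ((d√(n/2)-1.96)/√(1-R2))
- Power, adjusted: Φ(d√(n/2)/√(1-R2)-1.96)

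Example, R2=0.2 and d=0.5: √0.8 = 0.894. Unadjusted: Φ(0.276/0.894) = 0.621. Adjusted: Φ(2.236/0.894-1.96) = 0.705.

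| R2 | Type I, unadjusted | d=0.5, unadj. → adj. | d=0.628 | d=0.76 | d=1.0 |
|---|---|---|---|---|---|
| 0 | 0.050 | 0.609 → 0.609 | 0.802 → 0.802 | 0.925 → 0.925 | 0.994 → 0.994 |
| 0.1 | 0.039 | 0.614 → 0.654 | 0.814 → 0.841 | 0.935 → 0.948 | 0.996 → 0.997 |
| 0.2 | 0.028 | 0.621 → 0.705 | 0.829 → 0.881 | 0.946 → 0.967 | 0.998 → 0.999 |
| 0.3 | 0.019 | 0.629 → 0.762 | 0.845 → 0.919 | 0.957 → 0.982 | 0.999 → 1.000 |

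**4. Simulation with realistic, imperfect balance.** Assumed: 100 randomised by minimisation (biased coin 0.8), 20 lost at random, 80 analysed, one continuous outcome, linear model, p<0.05 trigger. Results at R2=0.1/0.2/0.3:
- Type I error under the rule: 4.1–4.5% / 3.2–3.8% / 2.9–3.4%. With the five factors and site pre-specified it is 4.7–5.2%.
- Unadjusted standard error too large by 2–4% / 4–9% / 7–12%.
- Power at d=0.5: 60% / 60% / 60–61% under the rule, against 63% / 67–68% / 73–74% adjusted.
- Power forgone at d=0.628: 1.4–2.1 / 5.0–5.6 / 8.2–9.2 points.
- Power forgone at d=0.76: about 1 / 3 / 4 points (0.8 / 2.3 / 3.9 in one set of runs). At d=1.0: 0.3 points or less.

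At R2=0.05 and d=0.5 the difference is 0.2–0.8 points. At R2=0, pre-specifying costs 1.3–2.1 points.

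**5. Urine results as outcome.** With 20 results per woman and an assumed 52–53% negative on placebo against 70% on guanfacine (d about 0.53), the power forgone at R2 of about 0.1/0.2/0.3 is 2.7–3.0 / 7.0–7.7 / 12.5–13.8 points in a linear model of percent negative. In a logistic model it is 2.8–3.2 / 7.4–8.0 / 13.2–14.7. The conclusion does not depend on the linear model.

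**6. Variables that are not balanced.** If 6/10/20 are tested (count assumed), the chance that at least one enters is 1-0.95ᵏ = 26% / 40% / 64% if independent, and 21% / 28% / 42% if correlated at 0.5. No effect on the estimate or on type I error was computed for this part.

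**The case against.** The strongest case against is that the harm rests on an R2 the documents do not give. Nothing in the document shows that the five factors predict drug use, and at R2 of 0.05 or less there is nothing to gain. That stands, and it makes this a conditional efficiency point. Severity of drug use is a plausible predictor of later drug use, but the document does not quantify it.

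The effect size matters too. This trial enrols only women, and at the women's pilot effect of d=1.0 adjustment changes essentially nothing. That also stands, although the pilot in Section II, B (Background Information) had only five women (two on guanfacine, three on placebo), so d=1.0 is weak support for planning.

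The text says that a variable which differs will be entered. It does not say that no other variable may be. That is correct: the firm statement is that this is the only covariate rule given, not that other terms are barred.

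Three stronger readings may tempt a reader, and the documents do not support them:
- **An excess of false positives.** The calculations show the opposite: type I error at or below 5%.
- **A fall below planned power.** Under balance the unadjusted test has slightly more power than a calculation without covariates (0.802 rises to 0.845 at d=0.628 and R2=0.3). The power is forgone relative to an adjusted analysis.
- **A material loss whenever R2 reaches about 0.2.** That holds only for effects near d=0.5 to 0.63.

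**Conclusion.** The point holds as a matter of efficiency and pre-specification, and should be fixed. Confidence is medium, because the size depends on inputs the plan does not give. A difference-triggered rule would almost never select the factors that the randomisation balances, and it leaves the choice of other covariates to chance. If the balancing factors are prognostic, the analysis is conservative. The power forgone ranges from negligible (R2 of 0.05 or less, or an effect as large as d=1.0) to about 13 points (R2=0.3 at d=0.5).

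The conclusion assumes that balancing works, that a difference means p<0.05, and that dropout is random. The mismatch between 40 per arm and the f=0.25 power claim is a separate issue, and this point does not rely on it.

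**What to change.** In Section I, 13 (Data Analysis), replace the sentence on entering variables that differ with:

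> Each efficacy model will include treatment, site and the randomisation balancing factors (age, education, race, ADHD, severity of drug use), coded as in the randomisation, whatever the baseline comparison shows. For outcomes measured before treatment (e.g. week-0 craving and Stroop), the pre-treatment value will also be included. Baseline comparisons are descriptive and will not determine covariates. The unadjusted result will be reported as a sensitivity analysis.

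The pre-treatment values will exist, because the laboratory "session will be conducted in the initial week of outpatient treatment Week 0, prior to medication, and again in Week 9". For this sentence to fix the model, the Randomization paragraph should also give the balancing method, the severity measure, the coding of each factor and whether site is a stratum.

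Cost: a wording change that needs no new data collection. The model uses 6 or 7 degrees of freedom out of 78, more if race or education has several levels. If the factors are not prognostic, power falls by about 1 to 2 points. If balancing also failed completely, the upper bound at d=0.5 is 3.4 points with six terms (0.598 to 0.564), 4.0 with seven (0.558) and 5.8 with ten (0.540).

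### The Holm step-down could replace single-step Bonferroni for the secondary outcomes: same 0.05 family-wise guarantee, no rejection lost, sometimes more gained (a free improvement, not an error)

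*Combined protocol and SAP*

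**What the plan says.** Section I, item 13, Data Analysis, treats the primary outcome on its own: "For the primary outcome, we will use significance level of 0.05". For the rest it says: "Significance levels for secondary outcomes will be adjusted using Bonferroni correction for number of analyses performed". No step-down, hierarchy or gatekeeping rule appears anywhere, and no simultaneous confidence intervals are planned.

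Adequacy of Sample Size, in the same item, carries the correction into power as a fixed per-test level: "Assuming an α level of 0.01 to correct for multiple tests for the secondary outcome measures". From that it concludes that "we can detect effects in the medium range ($f=0.28$) with 80% power for all the main effects for secondary outcome variables". The evaluable sample is given as "we will need 40 subjects per cell (Medgroup").

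The number of tests in the secondary family is not stated. A level of 0.01 equals 0.05/5 and so implies five. Study Assessments, item 3, names about 14 secondary instruments: four craving scales, four withdrawal scales, the ASI, the Treatment Services Review, the PSS, the Ham-A, the Ham-D and the Stroop.

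**The concern.** Bonferroni holds every secondary outcome to 0.05/m, even after others have been rejected. Holm orders the p-values and tests the smallest at 0.05/m, the next at 0.05/(m−1), and so on, stopping at the first failure. No Holm threshold is stricter than 0.05/m, so no Bonferroni rejection can be lost. Control of the family error at 0.05 needs no assumption about correlation.

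The questionnaire craving scales and the Stroop, which measure the targets the protocol hopes to engage, are in this family. The Background Information in Section II reports earlier effects in women on several cravings, anxiety, mood and Stroop performance. If several outcomes respond together again, a single-step rule may miss effects that Holm would confirm within the same 0.05 bound.

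**Working it through.** **Inputs.** From Adequacy of Sample Size: n = 40 per arm, f = 0.28, per-test level 0.01. For two groups d = 2f = 0.56. Assumed, because the documents do not say: two-sided tests, equal correlation of 0.3 to 0.5 between outcome statistics, the same effect on every responding outcome, and family sizes of 5 (implied by 0.01) and 14 (instruments named).

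**The plan's own figure first.** Noncentrality = d × √(n/2) = 0.56 × √20 = 2.504. At 0.01 two-sided the critical value is 2.576, so power = Φ(2.504 − 2.576) = Φ(−0.071) = 47%. The t-based value is 45%. The stated 80% does not reproduce from a plain two-group comparison. A repeated-measures calculation that the plan does not describe could lie behind it. With 14 tests the level is 0.05/14 = 0.0036, the critical value is 2.914, and power = Φ(2.504 − 2.914) = Φ(−0.409) = 34%.

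**Holm thresholds for five tests.** 0.05/5 = 0.010, 0.05/4 = 0.0125, 0.05/3 = 0.0167, 0.05/2 = 0.025, 0.05/1 = 0.05. Only the first equals the Bonferroni level; the others are more lenient.

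**Simulation.** 100,000 trials per setting, equicorrelated normal statistics, noncentrality 2.504 for each responding outcome, family level 0.05.

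| Family | Outcomes that respond | Average power per real outcome, Bonferroni | Holm |
|---|---|---|---|
| 5 | 1 | 47% | 47% |
| 5 | 3 | 47% | about 51% |
| 5 | 5 | 47% | 56% |
| 14 | 5 | 34% | 36% |
| 14 | 14 | 34% | 42–43% |

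With five of five responding, the chance of confirming all five goes from 9% to 26% at correlation 0.3, and from 15% to 34% at 0.5. The chance of confirming at least one is unchanged.

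**If the plan's 80% is taken at face value.** Scaling the noncentrality so that each test has 80% power at 0.01, with five tests and correlation 0.5: five of five responding, 80.0% to 88.2% per outcome; three of five, 80.0% to 83.2%; one of five, 79.8% under both.

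**Error.** With no real effects, the family error is identical under both methods and at most 0.05. With three of five real at the plain two-group power, it is about 0.019 under Bonferroni and about 0.031 under Holm. It stayed within 0.05 in every setting. Holm lost no Bonferroni rejection in any setting.

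**The case against.** The strongest reply is that nothing here is broken. Bonferroni is a valid, prestated rule, and its cost depends on how many outcomes respond. The protocol's hypothesis names craving and cognitive flexibility, which in Study Assessments means four craving scales and the Stroop: five of about 14 instruments. There the gain is only one to two points, and with seven of 14 responding it is still only 34% to 36–37%. The larger gains need most or all of the family to respond, and the documents do not define a five-outcome family. All of this stands, and it limits the size of the point.

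Three further objections also stand:

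- A reader might infer that Holm works at the same error rate. Only the bound is the same. The realised rate rises when some nulls are true. Bonferroni also caps the expected number of false rejections at 0.05, which Holm does not (0.054 in a run with five true nulls and correlation 0.5).
- A reader might infer that the quoted secondary power becomes a lower bound under Holm. The documents do not support this. The 0.01 level is Holm's first step only if the family has five tests. With 14 tests, Holm's average power (36% to 43% in the settings above) is below the 47% found at 0.01. The quoted 80% is itself not reproduced.
- The link to the aims is partial. Aim 2 asks whether changes in craving and flexibility predict drug use, which these treatment comparisons do not test. Laboratory craving is listed apart from the secondary measures.

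None of this removes the gain. Bonferroni's practical advantage, simple matching confidence intervals, is not used in this plan.

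**Conclusion.** This is a free improvement, not an error. Holm keeps the family-wise bound of 0.05 under any dependence and cannot lose a Bonferroni rejection, whatever the family size. How much it gains depends on the number of responding outcomes: nothing if one of five responds, about two points if five of 14 respond, and about nine points if all five of five or all 14 respond. These sizes rest on 40 evaluable women per arm for every outcome, f = 0.28, two-sided two-group tests and correlations of 0.3 to 0.5. Drug-specific scales that are informative only in a subset would have less power under either method.

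A reader might infer that the Bonferroni plan is invalid or that its secondary conclusions would be unsound. The documents do not support that reading: the plan is conservative, not wrong. The unstated family size and the unreproduced 80% are separate issues, and Holm settles neither.

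**What to change.** In Section I, item 13, Data Analysis, replace the Bonferroni clause with: the Holm step-down procedure at a family-wise level of 0.05 across the prespecified secondary outcomes, one p-value per outcome. Make the change before unblinding.

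The data, p-values and sample size do not change. The one-p-value condition means naming the outcomes in the family and a single test for each repeatedly measured one. Bonferroni needs a fixed count too, so this is not an extra burden caused by Holm. The only statistical cost is less simple simultaneous confidence intervals, should they be wanted later. Do not describe the power in Adequacy of Sample Size as a lower bound; resolve that figure separately.
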